### **5.3.5.10 Overdoses**

Study drug overdose is the accidental or intentional use of the drug in an amount higher than the dose being studied. An overdose or incorrect administration of study drug is not an adverse event unless it results in untoward medical effects.

Any study drug overdose or incorrect administration of study drug should be noted on the Study Drug Administration eCRF.

All adverse events associated with an overdose or incorrect administration of study drug should be recorded on the Adverse Event eCRF. If the associated adverse event fulfills serious criteria, the event should be reported to the Sponsor immediately (i.e., no more than 24 hours after learning of the event; see Section 5.4.2).

## **5.4 IMMEDIATE REPORTING REQUIREMENTS FROM INVESTIGATOR TO SPONSOR**

Certain events require immediate reporting to allow the Sponsor to take appropriate measures to address potential new risks in a clinical trial. The Investigator must report such events to the Sponsor immediately; under no circumstances should reporting take place more than 24 hours after the Investigator learns of the event. The following is a list of events that the Investigator must report to the Sponsor within 24 hours after learning of the event, regardless of relationship to study drug:

- Serious adverse events
- Non-serious adverse events of special interest
- Pregnancies

The Investigator must report new significant follow-up information for these events to the Sponsor immediately (i.e., no more than 24 hours after becoming aware of the information). New significant information includes the following:

- New signs or symptoms or a change in the diagnosis
- Significant new diagnostic test results
- Change in causality based on new information
- Change in the event's outcome, including recovery
- Additional narrative information on the clinical course of the event

Investigators must also comply with local requirements for reporting serious adverse events to the local health authority and IRB/EC.

### **5.4.1 Emergency Medical Contacts**

To ensure the safety of study subjects, access to the Medical monitors is available 24 hours a day, 7 days a week. *Medical monitors' contact details will be available on a separate list generated by the study management team.*

## **5.4.2 Reporting Requirements for Serious Adverse Events and Non-Serious Adverse Events of Special Interest**

### **5.4.2.1 Events That Occur prior to Study Drug Initiation**

After informed consent has been obtained but prior to initiation of study drug, only serious adverse events caused by a protocol-mandated intervention should be reported. The Serious Adverse Event/Adverse Event of Special Interest Reporting Form provided to Investigators should be completed and submitted to the Serious Adverse Event Responsible immediately (i.e., no more than 24 hours after learning of the event).

### **5.4.2.2 Events That Occur after Study Drug Initiation**

For reports of serious adverse events and non-serious adverse events of special interest (see Sections 5.1.2 and 5.1.3) that occur after initiation of study drug, investigators should record all case details that can be gathered immediately (i.e., within 24 hours after learning of the event) on the appropriate Serious Adverse Event / Adverse Event of Special Interest eCRF form and submit the report via the electronic data capture (EDC) system. A report will be generated and sent to the Sponsor's Safety Risk Management department.

In the event that the EDC system is unavailable, the Serious Adverse Event/Adverse Event of Special Interest Reporting Form provided to investigators should be completed and submitted to the Serious Adverse Event Responsible immediately (i.e., no more than 24 hours after learning of the event).

Once the EDC system is available, all information will need to be entered and submitted via the EDC system.

## **5.4.3 Reporting Requirements for Pregnancies**

### **5.4.3.1 Pregnancies in Female Healthy Volunteers**

Female subjects of childbearing potential will not be allowed to take part in this study. Although highly unlikely, female subjects will be instructed to immediately inform the Investigator if they become pregnant during the study or within 105 days after the last dose of study drug. A Clinical Trial Pregnancy Reporting Form should be completed by the Investigator and submitted to the Sponsor within 24 hours after learning of the pregnancy. Pregnancy should not be recorded on the Adverse Event eCRF. The Investigator should discontinue study drug and counsel the study subject, discussing the risks of the pregnancy and the possible effects on the fetus. Monitoring of the subject should continue until conclusion of the pregnancy.

### **5.4.3.2 Pregnancies in Female Partners of Male Healthy Volunteer**

Male subjects will be instructed through the Informed Consent Form to immediately inform the Investigator if their partner becomes pregnant during the study or within 105 days after the last dose of study drug. A Clinical Trial Pregnancy Reporting Form should be completed by the Investigator and submitted to the Sponsor within 24 hours after learning of the pregnancy. Attempts should be made to collect and report details of

the course and outcome of any pregnancy in the partner of a male HV exposed to study drug. The pregnant partner will need to sign an Authorization for Use and Disclosure of Pregnancy Health Information to allow for follow-up on her pregnancy. Once the authorization has been signed, the Investigator will update the Clinical Trial Pregnancy Reporting Form with additional information on the course and outcome of the pregnancy. An Investigator who is contacted by the male HV or his pregnant partner may provide information on the risks of the pregnancy and the possible effects on the fetus, to support an informed decision in cooperation with the treating physician and/or obstetrician.

#### **5.4.3.3      Abortions**

Any spontaneous abortion should be classified as a serious adverse event (as the Sponsor considers spontaneous abortions to be medically significant events), recorded on the Adverse Event eCRF, and reported to the Sponsor immediately (i.e., no more than 24 hours after learning of the event; see Section [5.4.2](#)).

Any induced abortion due to maternal toxicity and/or embryo-fetal toxicity should also be classified as serious adverse event, recorded on the Adverse Event eCRF, and reported to the Sponsor immediately (i.e., no more than 24 hours after learning of the event; see Section [5.4.2](#)).

Elective abortion not associated with toxicity (e.g., induced abortion for personal reasons) does not require expedited reporting but should be reported as outcome of pregnancy on the Clinical Trial Pregnancy Reporting Form.

#### **5.4.3.4      Congenital Anomalies/Birth Defects**

Any congenital anomaly/birth defect in a child born to a female HV or female partner of a male HV exposed to study drug should be classified as a serious adverse event, recorded on the Adverse Event eCRF, and reported to the Sponsor immediately (i.e., no more than 24 hours after learning of the event; see Section [5.4.2](#)).

### **5.5           FOLLOW-UP OF SUBJECTS AFTER ADVERSE EVENTS**

#### **5.5.1           Investigator Follow-Up**

The Investigator should follow each adverse event until the event has resolved to baseline grade or better, the event is assessed as stable by the Investigator, the HV is lost to follow-up, or the HV withdraws consent. Every effort should be made to follow all serious adverse events considered to be related to study drug or trial-related procedures until a final outcome can be reported.

During the study period, resolution of adverse events (with dates) should be documented on the Adverse Event eCRF and in the subject's medical records to facilitate source data verification. If, after follow-up, return to baseline status or stabilization cannot be established, an explanation should be recorded on the Adverse Event eCRF.

All pregnancies reported during the study should be followed until pregnancy outcome and reported according to the instructions provided in Section 5.4.3.

### **5.5.2 Sponsor Follow-Up**

For serious adverse events, non-serious adverse events of special interest, and pregnancies, the Sponsor or a designee may follow up by telephone, fax, electronic mail, and/or a monitoring visit to obtain additional case details and outcome information (e.g., from hospital discharge summaries, consultant reports, autopsy reports) in order to perform an independent medical assessment of the reported case.

## **5.6 POST-STUDY ADVERSE EVENTS**

The Investigator is not required to actively monitor subjects for adverse events after the end of the adverse event reporting period (defined as after the last follow-up visit).

If the Investigator becomes aware of any other serious adverse event occurring after the end of the adverse event reporting period, if the event is believed to be related to prior study drug administration, the event should be reported directly to the Sponsor or its designee, either by faxing or by scanning and emailing the Serious Adverse Event Reporting Form using the fax number or email address provided to Investigators.

### **5.7 EXPEDITED REPORTING TO HEALTH AUTHORITIES, INVESTIGATORS, INSTITUTIONAL REVIEW BOARDS, AND ETHICS COMMITTEES**

The Sponsor will promptly evaluate all serious adverse events and non-serious adverse events of special interest against cumulative product experience to identify and expeditiously communicate possible new safety findings to Investigators, IRBs, ECs, and applicable Health Authorities based on applicable legislation.

To determine reporting requirements for single adverse event cases, the Sponsor will assess the expectedness of these events using the following reference document:

- RO7062931 Investigator's Brochure

The Sponsor will compare the severity of each event and the cumulative event frequency reported for the study with the severity and frequency reported in the applicable reference document. Reporting requirements will also be based on the Investigator's assessment of causality and seriousness, with allowance for upgrading by the Sponsor as needed.

## **6. STATISTICAL CONSIDERATIONS AND ANALYSIS PLAN**

### **6.1 DETERMINATION OF SAMPLE SIZE**

The planned sample size of 8 active per cohort was chosen not only to allow adequate assessment of safety and tolerability but also to increase the precision of the estimates

of mean PK and urinary parameters, as comparisons of these parameters across doses will be used in part [REDACTED].

Up to 50 HVs will be included in this study. Up to 5 cohorts of 10 HVs (8 on active and 2 on placebo per dose level) are planned with the *fifth* and last cohort being optional and based on the analysis of emerging PK and safety data from this study and available data from study BP39405.

## **6.2 SUMMARIES OF CONDUCT OF STUDY**

Enrollment, major protocol violations and discontinuations from the study will be summarized by treatment and dose level. The number of HVs who were randomized, discontinued and completed the study will be summarized. Reasons for premature study withdrawal will be listed and summarized by treatment and dose level. Demographic and other baseline characteristics will be summarized with descriptive statistics by treatment and dose level. All HVs on placebo will be pooled as one treatment group.

## **6.3 ANALYSIS POPULATIONS**

### **6.3.1 Safety Analysis Population**

All HVs who have received one dose of the study medication, whether prematurely withdrawn from the study or not, will be included in the safety analysis.

### **6.3.2 Pharmacokinetic Analysis Population**

HVs will be excluded from the PK analysis population if they significantly violate the inclusion or exclusion criteria, deviate significantly from the protocol or if data are unavailable or incomplete which may influence the PK analysis. Excluded cases will be documented together with the reason for exclusion. All decisions on exclusions from the analysis will be made prior to database closure.

### **6.3.3 Immunogenicity Analysis Population**

The immunogenicity analyses, if applicable, will include subjects with a pre-dose and one post-dose ADA assessment, with subjects grouped according to treatment received.

The relationship between ADA status and safety and PK endpoints will be analyzed and reported descriptively via subgroup analyses.

## **6.4 SUMMARIES OF TREATMENT GROUP COMPARABILITY**

Descriptive statistics will be generated for demographics, including sex, self-reported race, ethnicity, age.

Data for study drug administration and concomitant medication will be listed. The number of subjects who were randomized, completed treatment period, discontinued study and completed the study (including follow-up period) will be summarized by treatment and dose level. All placebo patients will be pooled as one treatment group.

## **6.5 SAFETY ANALYSES**

All safety analyses will be based on the safety analysis population.

The safety data, including adverse events, injection site reactions (ISRs), reason for withdrawal from study, laboratory data, ECG, concomitant medications, vital signs and physical examination results will be listed and summarized descriptively by treatment and dose level. All placebo patients will be pooled as one treatment group. Marked abnormalities will be flagged for laboratory data.

As appropriate, listings, summary tables and graphs (study subject plot and/or mean plots) will be provided for safety and tolerability assessments.

### **6.5.1 Adverse Events**

The original terms recorded on the eCRF by the Investigator for adverse events will be standardized by the Sponsor by assigning preferred terms. Adverse events will be summarized by mapped term and appropriate thesaurus level.

Adverse events will be described by individual listings and frequency tables broken down by body system.

### **6.5.2 Clinical Laboratory Test Results**

All clinical laboratory data will be stored on the database in the units in which they were reported. Study subject listings and summary statistics at each assessment time will be presented using the International System of Units (SI units; Système International d'Unités). Laboratory data not reported in SI units will be converted to SI units before processing. Laboratory test values will be presented by listings and descriptive summary statistics.

#### **6.5.2.1 Standard Reference Ranges and Transformation of Data**

Roche standard reference ranges, rather than the reference ranges of the Investigator, will be used for all parameters. For most parameters, the measured laboratory test result will be assessed directly using the Roche standard reference range. Certain laboratory parameters will be transformed to Roche's standard reference ranges.

A transformation will be performed on certain laboratory tests that lack sufficiently common procedures and have a wide range of Investigator ranges, e.g., enzyme tests that include AST, ALT, and alkaline phosphatase and total bilirubin. Since the standard reference ranges for these parameters have a lower limit of zero, only the upper limits of the ranges will be used in transforming the data.

#### **6.5.2.2 Definition of Laboratory Abnormalities**

For all laboratory parameters included, there exists a Roche predefined standard reference range. Laboratory values falling outside this standard reference range will be labeled "H" for high or "L" for low in study subject listings of laboratory data.

In addition to the standard reference range, a marked reference range has been predefined by Roche for each laboratory parameter. The marked reference range is broader than the standard reference range. Values falling outside the marked reference range that also represent a defined change from baseline will be considered marked laboratory abnormalities (i.e., potentially clinically relevant). If a baseline value is not available for a study subject, the midpoint of the standard reference range will be used as the study subject baseline value for the purposes of determining marked laboratory abnormalities. Marked laboratory abnormalities will be labeled in the study subject listings as “HH” for very high or “LL” for very low.

#### **6.5.3 Vital Signs**

Vital signs data will be presented by individual listings. In addition, tabular summaries will be used, as appropriate.

#### **6.5.4 ECG Data Analysis**

ECG data will be reported as summary descriptive statistics for the actual values and changes from baseline will be tabulated by nominal time for HR, QRS duration, PR and QTcF. For multiple measurements taken at a nominal time-point, the average of these measurements will be used as the value at that nominal time-point in all summaries. In addition, QTcF will be categorized at each time-point as  $\leq 450$  msec,  $> 450\text{-}480$  msec,  $> 480\text{-}500$  msec and  $> 500$  msec and summarized. Similarly, a summary will be provided of the QTcF changes from baseline at each time-point categorized as  $< 30$  msec, 30-60 msec, and  $> 60$  msec. Changes of the overall ECG interpretation, T-wave and U-wave morphology will be summarized.

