### **3.1.2.2 Dose-Escalation Stopping Criteria**

Dose-escalation will not be implemented as planned if one of the criteria below is fulfilled, unless it is obvious that the occurrence is not considered to be related to RO7062931.

Dose-escalation will be stopped if at a dose level, more than 2 of 8 HVs receiving RO7062931 experience the following:

- Severe or clinically significant (as defined by the Investigator) RO7062931-related adverse events of the same character, or
- Clinically significant RO7062931-related laboratory abnormality of the same character, or
- Clinically significant RO7062931-related changes in vital signs or ECGs of the same character (e.g., QTcF > 500 msec, or > 60 msec longer than the pre-dose baseline, within the first 48 hours post-dose).
- Within two consecutive dose cohorts, four occurrences (in 4 HVs) of any of the above conditions in HVs receiving active drug.
- Other findings (regardless of the incidence rates) that at the joint discretion of the Sponsor and the Investigator indicate that dose-escalation should be halted.

Additionally, planned dose-escalation may be stopped by mutual agreement between the Sponsor and Investigator, [REDACTED]

In case the dose-escalation is stopped, lower doses within the tolerated dose-range could be investigated or a dose repeated in the subsequent cohorts by mutual agreement between the Sponsor and Investigator, in order to increase the amount of data within this tolerated dose-range.

*Any serious adverse event considered related to study drug will lead to an immediate halt of study drug dosing, dose escalation and enrollment of new subjects until a thorough investigation has been conducted by the Sponsor's Clinical Team and the Principal Investigator. The sponsor or designee will notify all investigators and IRBs/EC regarding the outcome of such investigation, and the study will only continue if agreed by the IRBs/EC.*

Due to the exploratory nature of this clinical study, its conduct can be discontinued at any time at the discretion of the Sponsor (see Section 4.7).

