#### **4.6.1.4      Electrocardiograms**

ECGs will be collected after the study subject has been in a supine position for at least 10 minutes prior to each ECG evaluation. At the specified time-points (see the Schedule of Assessments tables; [Appendix 1](#) and [Appendix 2](#)), 12-lead ECGs will be obtained in triplicate, i.e., three consecutive interpretable 12-lead ECGs within a 2-5-minutes, and recorded in eCRF. Triplicate recordings should be taken for any unscheduled ECG.

All ECG recordings must be performed using a standard digital high-quality, high-fidelity ECG machine equipped with computer-based interval measurements. Automated ECG intervals (PR [PQ], QRS, QT, QTcF [to be derived in eCRF]) and heart rate (HR) will be captured or calculated, and the changes in T-wave and U-wave morphology will be documented. Changes in T-wave and U-wave morphology and overall ECG interpretation will be documented on the eCRF. T-wave information will be captured as normal or abnormal, U-wave information will be captured in two categories: absent/normal or abnormal.

For safety monitoring purposes, the Investigator or designee must review, sign, and date all ECG tracings. Paper or electronic ECG tracings must be appropriately kept by the study center and must fulfill all applicable archiving requirements. The ECG intervals and interpretation will be recorded on the eCRF or may be sent electronically. If considered appropriate by Roche, ECGs may be analyzed retrospectively at a central laboratory.

The following are requirements for ECG assessments:

1. Digital ECG recordings, storage and analysis.
2. Three useful recordings must be collected without artefacts, per time-point.
3. Body position should also be consistently maintained for each ECG performed. In particular, changes in HR should be avoided. The absence of any environmental distractions (television, radio, conversation) during the pre-ECG rest and the ECG recording in the clinic must be emphasized.
4. Avoid (if the schedule of assessment allows) ECG recordings within 3 hours after meals.
5. Strictly match timing and conditions of ECG recording to baseline. Conditions to be standardized include food intake, activity level, stressors, and room temperature.
6. If possible, the same machine, brand and model, should be used for the same study subject throughout the study.
7. ECGs should be 12-lead, recorded at 25 mm/sec for at least 10 seconds.

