8. In some cases, it may be appropriate to repeat abnormal ECGs to rule out improper lead placement as contributing to the ECG abnormality.

9. ECG machines should have periodic calibration and service records (minimum once a year).
10. If any QT/QTc values > 500 msec or increases from pre-dose on Day 1 QTc > 60 msec (as provided by the machine), the site should repeat the ECG within the next 5 minutes and notify the Sponsor. If confirmed, ECG recordings should be repeated at least hourly until two successive ECGs show QTc values below the threshold value that triggered the repeated measurement.

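### QTcF outliers are counted only at scheduled ECG times, so a value found on an unscheduled ECG has no stated place in the > 500 msec or > 60 msec counts, and the handling of 5-minute alert repeats is left open

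*Combined protocol and SAP*

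**What the plan says.** Section 6.5.4 sets the time basis: "changes from baseline will be tabulated by nominal time for HR, QRS duration, PR and QTcF". Where there are several readings at a nominal time-point, "the average of these measurements will be used as the value at that nominal time-point in all summaries". The outlier displays are also per time-point. "In addition, QTcF will be categorized at each time-point as" introduces four bands that end at > 500 msec, and "QTcF changes from baseline at each time-point categorized as" introduces three bands that end at > 60 msec. No table of the maximum post-dose value or of the largest increase per subject is described.

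Section 4.6.1.4 generates ECGs outside that grid. After an alert (QT/QTc above 500 msec, or more than 60 msec above the Day 1 pre-dose value, as read by the machine), "the site should repeat the ECG within the next 5 minutes and notify the Sponsor". If the alert is confirmed, "ECG recordings should be repeated at least hourly until two successive ECGs show QTc values below the threshold value" that set it off. The section also says "Triplicate recordings should be taken for any unscheduled ECG".

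Section 3.1.2.2 gives "QTcF > 500 msec, or > 60 msec longer than the pre-dose baseline" within 48 hours of dosing as an example of a change relevant to stopping escalation. Section 6.5 says that ECG data will be listed as well as summarised.

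**The concern.** The category tables exist to show how many subjects at each dose, and on pooled placebo, had a marked QTcF value. The protocol deliberately collects more ECGs when something looks abnormal, yet the summary is built on a grid that does not contain the hours at which most of them fall. ECGs are one of the four safety outcome measures in Section 3.3.1, and safety compared with placebo is the primary objective. A table that reports zero subjects above 500 msec should mean that none was observed, not that none was observed at a scheduled hour.

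There is also an ambiguity. A repeat taken within 5 minutes could be read as one more measurement at the same nominal time-point and averaged in, or as an unscheduled ECG and left out. Two programmers following Section 6.5.4 could produce different tables from the same data.

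**Working it through.** **1. Scheduled ECGs against triggered ECGs**

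| Source | When an ECG is taken |
|---|---|
| Appendix 2, post-dose | 1, 4, 8, 12, 24 h; then none until Day 8 or a later visit |
| Section 4.6.1.4, after a confirmed alert | at least hourly |
| Section 3.1.2.2, window of the stopping example | first 48 h |

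Hourly repeats at 2-3, 5-7, 9-11 or 13-23 h have no ECG row. Nor does any unscheduled ECG between 24 h and 48 h, although the stopping example covers that period. (Appendix 1, as extracted, shows no ECG on Day 8 while Appendix 2 does; the point does not depend on which is right.)

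**2. An illustration (invented values)**

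Take triplicate means of 490 msec at 1 h, 504 at 2 h and 485 at 4 h. Hourly repeats need a confirmed alert, so if the 1 h value is the trigger it must be through the change criterion, which requires a pre-dose value below 490 − 60 = 430 msec. This subject is then already in the > 60 row at 1 h. The 504 at 2 h has no row, so the subject is tabulated as > 480-500 at 1 h and 4 h, and the > 500 count is zero. The increase at 2 h is 504 − 490 = 14 msec larger than the one tabulated at 1 h. So part of the signal is kept and part is not.

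**3. Weight of one subject**

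With 8 active subjects per dose (Section 6.1), 1/8 = 12.5 percentage points. This is the granularity of the table, not an estimate of error.

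**4. What pooling a 5-minute repeat would do**

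The plan gives no figure to reproduce. If a repeat triplicate is pooled, the time-point value is (scheduled mean + repeat mean)/2. A scheduled mean m above 500 drops to 500 or below when the repeat mean is at most 1000 − m: 497 for m = 503, 495 for m = 505, 490 for m = 510. Both directions are possible:

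- 504/503/502 (mean 503.0) with repeat 492/494/493 gives 498.0: moves down to > 480-500.
- 504/494/495 (mean 497.7) with repeat 506/505/507 gives 501.8: moves up to > 500.

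The change from baseline was simulated with 400,000 time-points per setting. Assumptions, none of them in the documents: single-reading SD 5 msec; occasion SD 4, 6 or 8 msec; correlation 0.5 between the two occasions; a repeat triplicate added whenever any scheduled reading exceeds 60 msec.

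| True change (msec) | Share > 60, scheduled triplicate only (occasion SD 4/6/8) | Share > 60, repeat pooled |
|---|---|---|
| 55 | 15.6 / 22.6 / 27.8% | 10.0 / 17.2 / 22.5% |
| 65 | 84.5 / 77.4 / 72.3% | 88.0 / 79.4 / 72.9% |

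The bias in the time-point mean was negative throughout (true changes of 45 to 70 msec) but always smaller than 1 msec. It arises because extra readings are added only after a high one. The count of outliers falls when the true change is below the threshold and rises when it is above.

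**The case against.** The strongest objection is that nothing is concealed. ECG data are listed under Section 6.5, every alert is notified to the sponsor, ECGs are reviewed before each escalation, and with 8 active subjects per cohort a reader can find an outlier in a listing. Section 6.5.4 writes no exclusion of unscheduled ECGs, and its summary of overall ECG interpretation and wave morphology is not tied to nominal time. A subject with a confirmed alert at a scheduled hour will often be in an outlier row already. All of this stands, and it limits the consequence. It does not supply the missing count: a listing does not give incidence by dose against pooled placebo, and the only QTcF categories planned are per time-point.

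A reader might infer that the averaging rule makes outlier counts too low in every case, and most of all where the drug prolongs QTcF. The documents do not support this. They do not say that a 5-minute repeat belongs to the nominal time-point, and if it is treated as unscheduled there is no dilution. Even if it is pooled, the counts move in both directions, upward when the true change exceeds the threshold. Averaging the planned triplicate is sound practice, and pooling also reduces noise in the mean.

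A reader might also infer that the stopping criterion and the tables are in conflict. They serve different purposes. Section 3.1.2.2 asks for a judgement on clinically significant, drug-related changes of the same character in more than 2 of 8 subjects, not a count read from the table. Likewise, alerts use machine QT/QTc, whereas the tables use QTcF derived in the eCRF, so the two need not match.

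**Conclusion.** The point holds as a gap in the summary of outliers. As written, Section 6.5.4 gives no place in the > 500 msec or > 60 msec counts to a QTcF value obtained between scheduled times, including between 24 and 48 h, and it plans no worst post-dose summary. This follows from the text and Appendix 2 and needs no assumption about variability. It would be too strong to say that these ECGs are reported nowhere, since they would be listed.

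The pooling question is a secondary ambiguity. Under the assumed SDs it is worth less than 1 msec in the mean and changes category counts in either direction. The number of triggered ECGs is not given and may be small in healthy volunteers, so the practical effect could be nil. When it is not, each affected subject is one in eight at that dose. The change is worth making because it is cheap and concerns a named safety outcome.

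**What to change.** In Section 6.5.4:

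- (a) Define the value at a nominal time-point as the mean of the scheduled triplicate only. State that confirmatory and other unscheduled ECGs are not averaged into it.
- (b) Add a per-subject table of the highest post-dose QTcF and the largest increase from pre-dose, using the existing categories, over all scheduled and unscheduled triplicates with each triplicate averaged first. Present it by dose with pooled placebo, and label it as including unscheduled ECGs.

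The cost is a few lines of text and one extra table from ECGs that Section 4.6.1.4 already requires to be recorded. No change to ECG collection, alerts or escalation rules is involved. The downside is that subjects with triggered repeats contribute more readings to the worst-value table and so have more chances of a high value. The label and the unchanged per-time-point tables alongside let the reader allow for that.
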